7.2.6. Observation period

7.2.6.1. Observation period

One year (52 weeks) from the start date of administration.

However, in patients who discontinue treatment with this drug, the period will be from the start date of administration to the first consultation day after the discontinuation day of treatment with this drug.

[figure not shown]

Figure 1. Observation Period for Each Booklet

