7.3.3. Whether or not treatment with this drug is continued

- 1. Whether or not treatment with this drug is continued
- 2. First consultation day after the discontinuation day of treatment with this drug
- 3. Reason for discontinuation of treatment with this drug

A6141122 NON-INTERVENTIONAL STUDY PROTOCOL

Amended1, 01 December 2018

If treatment with this drug is not continued until the last day of the observation period in this study, select and enter the reason for it from among the following. If any adverse event is selected, enter its details in the section of adverse events. If other is selected, enter the reason for it as well.

- 1. Insufficient clinical effectiveness
- 2. Adverse event
- 3. No re-visit a)
- 4. Other b)
- a. Enter it only in Booklet 02.
- b. If "Other," enter the reason for it; for example, the patient's will unrelated to the adverse event.

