5.4. Subgroup Analyses

The safety of study drug will be analyzed for each of the subgroups defined according to the following patient characteristics. The underlined one in each categorization will be used as the reference when a risk ratio is calculated:

- Hepatic impairment (as assessed by the physician) (present, absent, unknown)
- Renal impairment (as assessed by the physician) (present, absent, unknown)
- Estimated creatinine clearance (eCLCr)
 (<30 mL/min, 30 mL/min <50 mL/min, ≥50 mL/min, unknown)
- Not aged (<65 years old), Aged (≥65 years old)
- Children (<15 years old), Not children (≥15 years old)
- Young-old (\geq 65, <75 years old), Old-old + oldest-old (\geq 75 years old)
- Diabetes mellitus with microalbuminuria or proteinuria (present, absent, unknown)

Safety will also be analyzed for each of the subgroups defined according to the following factors:

- Use of a relevant treatment for CHF/hypertension (present, absent) (any of the 1st to 17th drug groups, except the 2nd and 15th which are contraindicated for coadministration, listed)
- Previous treatment with device therapy (present, absent, unknown)

NYHA class (I, II, III, IV, not assessed/unknown)

As a subgroup analysis, patients who may have violated any of the contraindications indicated in the package insert of Selara Tablets ("contraindication violators", hereinafter) will be extracted according to the criteria defined separately and the safety will be assessed for this subgroup.

The effectiveness of study drug will be analyzed for each of the subgroups defined according to the following patient characteristics:

- Hepatic impairment (as assessed by the physician) (present, absent, unknown)
- Renal impairment (as assessed by the physician) (present, absent, unknown)
- Estimated creatinine clearance (eCLCr)
 (<30 mL/min, 30 mL/min <50 mL/min, ≥50 mL/min, unknown)
- Not aged (<65 years old), Aged (≥65 years old)
- Children (<15 years old), Not children (≥15 years old)
- Young-old (\geq 65, <75 years old), Old-old + oldest-old (\geq 75 years old)
- Use of a relevant treatment for CHF/hypertension (present, absent)
- NYHA class (I, II, III, IV, not assessed/unknown)
- Treatment status (completed, discontinued)

If patients included in a subgroup for safety or effectiveness analysis are limited, reviewing individual patients will be considered instead of presenting a statistical summarization.

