8.1.4. Time-to-event Data

Mortality at one year from the start of treatment will be estimated using the Kaplan-Meier method. Kaplan-Meier plots (displaying the number of at-risk patients every one month) will also be presented.

Analyses Based on the Person-Year Method

The incidence of an event per observation time will, if it is presented, be calculated using the formula:

Incidence (events/100 person-year) = $100 \times y/PT$ y: Number of events PT: Total observation time (years),

where the observation time is determined in conformity with the part "Follow-up Status" in "8.2.2. Patient Characteristics and Medical History". In addition, its 95% CI will be presented according to the formula ¹:

$$\left[\frac{100}{PT} \times \frac{1}{2} \chi_{2y}^{2}(\alpha/2), \frac{100}{PT} \times \frac{1}{2} \chi_{2(y+1)}^{2}(1-\alpha/2)\right]$$

y: Number of events

 $\chi^2_{2y}(\alpha/2)$: The $\alpha/2$ percentage point of the chi-square distribution of 2y degrees of freedom

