8.2.4. Effectiveness Analyses

8.2.4.1. Death

Deaths will be summarized in terms of number and proportion of patients by cause of death (cardiovascular, non-cardiovascular, unknown) and detailed cause of death (cardiovascular: cardiac failure, myocardial infarction, arrhythmia, stroke or cerebrovascular accident, others; non-cardiovascular: neoplasm malignant, infection, others).

All-cause deaths and cardiovascular deaths will be analyzed in the following manner:

- "8.1.3. Binary Variables" will be followed for binary variables, and
- "8.1.4. Time-to-event Data" will be followed for time-to-event data.

In the Kaplan-Meier analysis, a patient whose date of death is unknown will be handled as follows:

➤ If the date of final confirmation of survival is on Week 52 or earlier and the information of death was obtained on Week 52 or earlier,

the patient is handled as interval censored data between the date of final confirmation of survival and the date of death information:

If the date of final confirmation of survival is on Week 52 or earlier and the information of death was obtained after Week 52.

the patient is handled as a patient who was alive on the date of final confirmation of survival;

➤ If the date of final confirmation of survival is after Week 52 and the information of death was obtained after Week 52,

the patient is handled as a patient who was alive at Week 52 (Day 364).

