8.2.4.4. Subgroup Analyses

According to the categorizations defined in Section 5.4, subgroup analyses will be performed regarding deaths and clinical effectiveness (as assessed by the physician).

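### Deaths are to be tabulated by treatment status, a grouping fixed after baseline that depends on survival, so completers show zero mortality to Week 52 whatever the drug does

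*SAP*

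**What the plan says.** SAP 5.4 introduces the effectiveness subgroups with "The effectiveness of study drug will be analyzed for each of the subgroups defined according to the following patient characteristics". The last item on the list is "Treatment status (completed, discontinued"). It has two levels, with none for patients who died and none for unknown status.

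SAP 8.2.4.4 then says: "According to the categorizations defined in Section 5.4, subgroup analyses will be performed regarding deaths and clinical effectiveness (as assessed by the physician"). No grouping is exempted for deaths.

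On deaths, SAP 8.2.4.1 begins "All-cause deaths and cardiovascular deaths will be analyzed in the following manner" and points to the methods for binary and for time-to-event data. SAP 8.1.4 says "Mortality at one year from the start of treatment will be estimated using the Kaplan-Meier method" and adds a person-year rate.

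The SAP does not define completed. The protocol supplies the elements. Section 7.2.6.1 sets the observation period as "One year (52 weeks) from the start date of administration" and shortens it only for patients who discontinue. Section 7.3.3 asks for a reason "If treatment with this drug is not continued until the last day of the observation period in this study". The opening of SAP section 8 gives patients who completed treatment a data window of 364 + 30 days. It has one rule for patients who discontinued and another, inclusion of all data, for patients who died.

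**The concern.** All other effectiveness groupings in SAP 5.4 describe the patient at or around entry, or the background treatment. Treatment status is settled only during follow-up, and being alive is a condition for one of its levels. Mortality counted from Day 1 but split by such a status credits completers with a full year during which they could not have died.

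SAP section 3 says that every analysis in the plan will be run at the final analysis for re-examination. A reader of that output would see no deaths by Week 52 among completers beside some deaths among discontinued patients, and could take this for a benefit of staying on the drug. Neither the SAP nor protocol 7.9 (limitations) cautions against that reading.

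**Working it through.** **Inputs.** The documents give no mortality figure by treatment status, so there is none to reproduce. One-year all-cause mortality m is 7.3% or 8.9% (protocol 7.2.6.2, two domestic cohorts), and the sample size is 1000 (protocol 7.5.1). The documents give no discontinuation rate. I assume that D = 15%, 25% or 35% of patients are discontinued by Week 52, deaths included, and that survival follow-up to Week 52 is complete.

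**Step 1: the zero.** A completer has continued treatment to the last day of a 52-week period. A patient who dies before that day has not. Completers' deaths to Week 52 are therefore 0, whatever m, D or the drug effect. This step needs none of the assumed values.

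**Step 2: on-drug deaths placed in discontinued.** All 1000m deaths (73 or 89) fall among 1000D patients, so that group's mortality is m/D.

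| D | Completed | Discontinued, m = 7.3% | Discontinued, m = 8.9% |
|---|---|---|---|
| 15% | 0/850 | 73/150 = 48.7% | 89/150 = 59.3% |
| 25% | 0/750 | 73/250 = 29.2% | 89/250 = 35.6% |
| 35% | 0/650 | 73/350 = 20.9% | 89/350 = 25.4% |

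**Step 3: how much of this is artefact.** Let the death hazard be the same on and off drug, so that stopping has no effect on mortality. With 364 days as the time unit, h = −ln(1 − m) = 0.0758 or 0.0932. The stopping hazard s solves exp(−(h + s)) = 1 − D. Deaths on drug are 1000·D·h/(h + s).

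- m = 7.3%: 70.0, 65.9 and 61.6 of 73 for D = 15%, 25% and 35%.
- m = 8.9%: 86.0, 81.0 and 75.7 of 89.

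So 84% (61.6/73) to 97% (86.0/89) of the deaths shown as discontinued happened while the patient was still on the drug.

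**Step 4: on-drug deaths kept apart.** The discontinued group then holds only patients who were alive when they stopped. Its mortality is (1000m − on-drug deaths)/(1000D − on-drug deaths).

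- m = 7.3%: D = 15%, 3.04/80.04 = 3.8%; D = 35%, 11.41/288.41 = 4.0%.
- m = 8.9%: D = 15%, 2.97/63.97 = 4.6%; D = 35%, 13.27/274.27 = 4.8% (4.9% from the rounded 13.3/274).

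Completers remain at 0%. Both groups now lie below the true 7.3% or 8.9%, because the on-drug deaths are in neither.

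**Step 5: the same data with status updated in time.** Person-time on drug is 1000·D/(h + s), total person-time is 1000·m/h, and the remainder is time after stopping.

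- m = 7.3%, D = 15%: on drug 70.0/923.0 = 7.6 per 100 person-years; after stopping 3.04/40.1 = 7.6.
- m = 7.3%, D = 35%: 61.6/812.5 = 7.6 and 11.4/150.6 = 7.6.
- m = 8.9%, D = 15%: 86.0/923.0 = 9.3 and 2.97/31.8 = 9.3.
- m = 8.9%, D = 35%: 75.7/812.5 = 9.3 and 13.3/142.3 = 9.3.

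The difference disappears, as it should under equal hazards.

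**Simulation check.** One million patients per scenario, with 10%–40% stopping for reasons other than death and on-drug deaths counted as discontinued, gave completer mortality of 0 in every scenario. Discontinued mortality was 16.5%–44.1% (m = 7.3%) and 19.6%–49.7% (m = 8.9%).

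**The case against.** The strongest objection is that the plan never says where an on-drug death goes. Protocol 7.3.3 does not list death as a reason for stopping, and SAP section 8 treats patients who died separately from the other two kinds. This stands in part. A reader might infer that the SAP assigns every death to Week 52 to the discontinued group, but it does not. The section 8 rule decides which data are used and gives no treatment status. Placement in discontinued is the natural result of having two levels, and the 20.9%–59.3% range depends on it.

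Could on-drug deaths be coded as completed? The direction would then reverse: in the same model, completers would show about 7.6% (70.0/920.0) to 10.4% (75.7/725.7), against 3.8%–4.8%. No text supports this coding. The protocol shortens the 52-week period only for patients who discontinue, so a patient who died on drug has not been treated to its last day.

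Three further points stand. The sizes follow from an assumed D; 59.3% requires only 61 of 1000 patients (150 − 89) to be discontinued other than through death. Kaplan-Meier by subgroup is the natural reading of 8.2.4.4 with 8.2.4.1, but it is not stated; counts and proportions to Week 52 would show the same zero. A completer's death after Week 52 might enter a binary count, since all data are used for patients who died, so the zero is claimed only to Week 52.

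The SAP also calls its tests exploratory (4.1), and it reports discontinuations by reason and lists deaths elsewhere. That limits the harm but does not make this table informative. The 5.4 provision for reviewing individual patients concerns small subgroups, which is a different problem.

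**Conclusion.** The point holds. Splitting mortality from the start of treatment by completed versus discontinued gives completers 0% to Week 52 by construction, on the natural reading of protocol 7.2.6.1 and 7.3.3 and SAP section 8. The discontinued figure depends on an unstated assignment: 20.9%–59.3% if on-drug deaths go there, about 3.8%–4.8% if they are kept apart. Both ranges rest on 7.3%–8.9% overall mortality, an assumed 15%–35% discontinued including deaths, and complete survival follow-up; the lower range also assumes constant, equal, independent hazards. Under either assignment the table cannot inform on effectiveness.

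A reader might go further and infer that the mortality results as a whole, or the safety conclusions, are compromised. The documents do not support that. Overall mortality does not use this grouping, treatment status is not a safety subgroup in SAP 5.4, and 8.2.4.4 specifies no formal contrast. The impact is one exploratory, descriptive cut of a secondary objective. It should be corrected because it invites a false reading and the correction is small.

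**What to change.** State in SAP 8.2.4.4 that treatment status is not applied to deaths. The cost is one sentence and the loss of one exploratory table. SAP version 7.0 records observation as completed; no new data are needed, and the table can still be dropped at reporting.

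If deaths in relation to treatment are wanted, report deaths and person-time on treatment and after stopping as a time-updated state, using the dosing and survival dates already collected (protocol 7.3.2 and 7.3.9). Label the result descriptive, because reasons for stopping confound it. This needs some extra programming and its own rules for deaths near the last dose and for unknown last-dose and death dates. The existing rules should not be carried over unchanged. SAP 8.2.2 sets an unknown last dose to the first visit after discontinuation, which would count off-drug time as on-drug, and a patient who died may have no such visit. The interval-censoring rule in SAP 8.2.4.1 is written for Kaplan-Meier, not for person-time by state.

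If treatment status is kept for physician-assessed effectiveness, label that table descriptive as well, since "Insufficient clinical effectiveness" is itself a listed reason for stopping (protocol 7.3.3).

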6. ENDPOINTS AND COVARIATES

6.1. Safety Endpoints

- Adverse reactions: An adverse reaction is an AE related to study drug as judged by the physician.
- Serious adverse reactions: A serious adverse reaction is an adverse reaction that is serious as judged by the physician.
- AEs
- Serious adverse events (SAEs): A SAE is an AE that is serious as judged by the physician.
- Major investigation items: Events included in each major investigation item are defined as follows:
 - Hyperkalaemia: This includes all AEs indicated as "Hyperkalaemia-related event" or "Combination of the above two events ("Hypotension-related event" and "Hyperkalaemia-related event")" in the CRF.

Hypotension-related events: These include all AEs indicated as "Hypotension-related event" or "Combination of the above two events ("Hypotension-related event" and "Hyperkalaemia-related event")" in the CRF.

- Other investigation items
 - Renal impairment-related events

Renal impairment-related events are events coded as one of the following preferred terms (PTs):

Acute kidney injury, Chronic kidney disease, Renal failure, or Renal impairment.

- Blood pressure (systolic, diastolic)
- Body weight
- Laboratory tests (serum creatinine, serum potassium, BUN)

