7.7. Data analyses

1) Definition of analysis sets

The safety analysis set (SAS) is defined as patients in whom treatment with this drug was confirmed.

The efficacy analysis set is defined as patients in whom treatment with this drug was confirmed and the efficacy could be evaluated in CHF patients.

2) Method of Analysis

(1) Safety analysis

Events for which a causal relationship with this drug cannot be ruled out will be handled as adverse reactions, and the number and proportion of cases of adverse reactions will be aggregated by System Organ Class and Preferred Term.

For patients with renal impairment, moderate renal impairment, or hepatic impairment, elderly patients (\geq 65 years, \geq 75 years), pediatric patients (<15 years), and diabetes patients with micro albuminuria or proteinuria, the safety will be comparatively investigated versus other populations.

In addition, the occurrence status of adverse reactions related to hyperkalaemia, renal impairment, or blood pressure decreased will be investigated in terms of risk factors and onset time.

(2) Efficacy analysis

Regarding each evaluation item for clinical evaluation, the number and proportion of cases will be aggregated by level from the results. Regarding the overall mortality and cardiovascular deaths in the study, the number of deaths and death rate (%), death rate (%) after 1 year observation period, death rate based on person-year method (the number of deaths in 100 person-year) will be calculated. For reference, the results will be compared to the domestic Phase III study or Japanese epidemiological surveys (CHART-1, CHART-2, JCARE-CARD, etc.). These comparisons will be performed with adjustment of factors such as patient background that are considered available or appropriate at the time of evaluation or setting of appropriate subgroups. ^{a)}

a. For the domestic Phase III study, comparisons to death rates adjusted for age, gender, and NYHA Functional Classification by using individual data such as patient background collected in the study will be considered; and for the Japanese epidemiological surveys, comparisons to death rates adjusted for gender and NYHA Functional Classification by using aggregate data such as patient background from published papers, etc. will be considered.

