9.3. Causality assessment

The investigator is required to assess and record the causal relationship. For all AEs, sufficient information should be obtained by the investigator to determine the causality of each AE. For AEs with a causal relationship to this drug, follow-up by the investigator is required until the event and/or its sequelae resolve or stabilize at a level acceptable to the investigator, and Pfizer concurs with that assessment.

Selara A6141122 NON-INTERVENTIONAL STUDY PROTOCOL Amended 1, 01 December 2018

An investigator's causality assessment is the determination of whether there exists a reasonable possibility that this drug caused or contributed to an AE. If the investigator's final determination of causality is "unknown" and s/he cannot determine whether this drug caused the event, the safety event must be reported within 24 hours.

If the investigator cannot determine the etiology of the event but s/he determines that this drug did not cause the event, this should be clearly documented in the data collection tool (e.g. CRF) and the NIS AE Report Form.

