7. HANDLING OF MISSING DATA

If the severity, treatment, or outcome of an AE is missing, it will be regarded as having a value of "unknown" at the time of a statistical summarization.

If an observation for the dosing status, a safety endpoint, an effectiveness endpoint, or a laboratory test was done outside its time window (Appendices A1.1, A1.2, and A1.3), the obtained data will be regarded as missing data and will not be imputed.

Cleaning-uncompleted data will be basically handled as follows. Detailed handling of individual items will be explained in separate lists.

• Items for which data are missing: For both summarization and listing, their values will be handled as missing data (or "unknown" in the case of a categorical variable).

- Items for which data are inconsistent: For both summarization and listing, their values will be handled as missing data.
- Items for which signature is missing: For both summarization and listing, any data in a CRF with no signature of the contract physician (including when the CRF is signed only by individuals other than the contract physician) will be handled as missing data.

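### SAP 6.1 defines an adverse reaction more narrowly than protocol 7.7 and does not say where events of unknown or missing causality belong

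*SAP*

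**What the plan says.** The protocol's rule is in section 7.7: "Events for which a causal relationship with this drug cannot be ruled out will be handled as adverse reactions". Section 7.5.2 uses the same criterion for Table 5 and for every planning rate derived from it.

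The SAP's rule is in section 6.1: "An adverse reaction is an AE related to study drug as judged by the physician". A serious adverse reaction is then an adverse reaction that the physician also judges serious, so it inherits the same condition.

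Protocol 9.3 asks the investigator to judge "whether there exists a reasonable possibility that this drug caused or contributed to an AE". It also provides for a final causality of *unknown*: where the investigator "cannot determine whether this drug caused the event, the safety event must be reported within 24 hours". That sentence sets a reporting duty. It does not say how the event is classified for analysis.

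On missing data, SAP section 7 has a rule that begins "If the severity, treatment, or outcome of an AE is missing"; causality is not in that list. A general rule for data whose cleaning was not completed treats missing items as missing, or as *unknown* if categorical, and inconsistent items as missing.

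**The concern.** The two definitions agree on an event judged related and on an event judged unrelated. They part on an event that the physician could not decide about. Causality has not been ruled out, so protocol 7.7 counts the event. The physician has not called it related, so the literal SAP wording does not.

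This matters because adverse reactions carry the subgroup analyses. The primary objective is safety in moderate renal impairment. SAP 8.2.3.4 addresses it through adverse reactions, serious adverse reactions and SAEs within the groups of SAP 5.4, including creatinine clearance of 30 to under 50 mL/min. If undecided events fall outside the definition, that incidence is read too low, and it no longer matches the criterion behind the planning rates.

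**Working it through.** **Step 1. Classify an AE under each rule.**

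| Causality recorded | Protocol 7.7 | SAP 6.1, literal reading |
|---|---|---|
| Related | Adverse reaction | Adverse reaction |
| Judged not caused by the drug | Not counted | Not counted |
| Unknown, cannot be determined | Adverse reaction (not ruled out) | Not counted |
| Missing | No explicit rule, but nobody has ruled it out | Not counted; at most set to *unknown* by SAP 7 |

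Protocol 9.3 itself separates rows 2 and 3. An investigator who does not know the cause but is satisfied that it was not the drug must document that. This differs from being unable to say whether the drug was responsible.

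**Step 2. Trace an AE of unknown causality through the SAP.**

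| Analysis | Non-serious AE | Serious AE |
|---|---|---|
| Adverse reactions by SOC and PT (8.2.3.1) | Absent | Absent |
| Serious adverse reactions (8.2.3.1) | Does not apply | Absent |
| All AEs; SAEs and non-SAEs (8.2.3.2) | Present | Present |
| Hyperkalaemia, hypotension and renal items as defined in 6.1 | Present if flagged or coded | Present if flagged or coded |
| Subgroups: adverse reactions and any risk ratio (8.2.3.4) | Absent | Absent |
| Subgroups: serious adverse reactions (8.2.3.4) | Does not apply | Absent |
| Subgroups: SAEs (8.2.3.4) | Does not apply | Present |

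A non-serious event of unknown causality in a patient with creatinine clearance of 30 to under 50 mL/min therefore appears in no subgroup incidence table. The all-AE tables and the hyperkalaemia, hypotension and renal tables are not specified by creatinine clearance.

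**Step 3. Reproduce the protocol's planning figures (7.5.2).** These rest on the broader definition.

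- Pooled rates: 8/261 = 3.07% (renal) and 22/261 = 8.43% (hyperkalaemia), stated as 3.1% and 8.4%.
- Expected patients, N × p: 300 × 0.031 = 9.3 and 300 × 0.084 = 25.2; 350 × 0.031 = 10.85 and 350 × 0.084 = 29.4.
- Approximate 95% range at N = 300, p ± 1.96 × √(p(1−p)/N): 1.14% to 5.06% and 5.26% to 11.54%, stated as 1.1%–5.1% and 5.3%–11.5%.
- All CHF patients, N = 1000: 1000 × 0.012 = 12.0 and 1000 × 0.040 = 40.0. The 2.5% and 97.5% binomial quantiles are 6–19 and 28–53.

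All agree with the protocol. The sample-size arithmetic is not in question.

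**Step 4. Illustrate the loss.** The documents give no share u of not-ruled-out events whose causality is unknown or missing, so u is an assumption. The count is N × p × (1−u), for adverse reactions of each type in 300 patients with moderate renal impairment:

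| Assumed u | Hyperkalaemia reactions | Renal reactions |
|---|---|---|
| 0% | 25.2 (8.4%) | 9.3 (3.1%) |
| 10% | 22.7 (7.6%) | 8.4 (2.8%) |
| 20% | 20.2 (6.7%) | 7.4 (2.5%) |
| 30% | 17.6 (5.9%) | 6.5 (2.2%) |

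These figures apply to adverse-reaction counts only, not to the hyperkalaemia or renal items as SAP 6.1 defines them. Every value lies inside the protocol's own approximate 95% range at N = 300. The shift is nevertheless systematic and in one direction for incidence. A risk ratio could move either way, depending on how u differs between subgroups.

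**The case against.** The strongest reply is that the gap may be one of wording alone. The documents do not show the CRF causality categories; protocol 7.3.8 says only that the causal relationship is recorded. If the item is a yes/no answer to the reasonable-possibility question in protocol 9.3, *related* and *cannot be ruled out* may coincide, and no event is lost. This stands. It makes the size unknown, but it does not remove the conflict, because protocol 9.3 also foresees *unknown* as a final answer.

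A reader might infer that the SAP ignores every event not judged related. It does not: all AEs and SAEs are tabulated, and SAP section 9 lists both the events and the adverse reactions of the hyperkalaemia, hypotension and renal items. A reader might also infer that the hyperkalaemia item itself would fall below 8.4%. As SAP 6.1 defines it, that item takes all flagged AEs with no causality condition, and the renal item is defined by preferred term alone. What remains unclear is whether their placement under the Adverse Reactions heading of 8.2.3.1 restricts those tables.

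Nor do the documents show an intended narrowing. The SAP revision history describes the version 2.0 change to the definition as removing company judgement. Protocol 7.7 requires an amendment for major changes to primary endpoint definitions, and none is recorded on this point. Loose shorthand is a plausible explanation.

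Finally, the SAP plans no formal comparison of adverse-reaction rates with the Phase III studies; its external comparisons concern death. Protocol 7.5.2 speaks only in general terms of evaluating the safety profile between clinical studies and use-results surveys. The documents therefore do not support a claim that a prespecified comparison is biased.

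**Conclusion.** The point holds in limited form. The SAP's definition is narrower in wording than protocol 7.7 and the planning rates, and the SAP has no rule that places unknown or missing causality on one side or the other. Its general missing-data rule yields at most *unknown*, which is still not *related*.

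On the literal reading, the affected results are the adverse-reaction and serious-adverse-reaction tables, the corresponding subgroup incidences, and any risk ratios built on them. Overall AE and SAE tables are unaffected, as are the hyperkalaemia, hypotension and renal items as defined.

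The direction for adverse-reaction incidence is certain: it can fall or stay the same, not rise. The size is not known. It runs from nil, if the CRF forces a yes/no judgement, to the assumed losses in the last table of the working. The conclusion rests on the literal reading of SAP 6.1 and on *unknown* or missing being possible CRF states. The change is worth making because the subgroup tables serve the primary objective.

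**What to change.** 1. Restate SAP 6.1 to match protocol 7.7: an adverse reaction is an AE whose causal relationship with the drug cannot be ruled out, that is, any AE the physician did not judge unrelated.
2. State in SAP 6.1 and section 7 that unknown or missing causality counts as not ruled out, and that this also applies to serious adverse reactions.
3. State whether the hyperkalaemia, hypotension and renal tables under SAP 8.2.3.1 count all AEs or adverse reactions only.
4. Report the number of AEs with unknown or missing causality, overall and by creatinine-clearance group, with a sensitivity table that excludes them. This shows the size directly.

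The cost is a few sentences in the SAP and a small programming change. No new data are needed, because causality is already a CRF item. Adverse-reaction incidence may come out slightly less favourable. If no event has unknown or missing causality, the adverse-reaction results do not change.
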